10.7. Safety Analysis

10.7.1. Toxicity Assessment

Toxicity will be monitored real-time through study chair notification and end of course reports. Descriptive statistics will be used to summarize the proportion of subjects experiencing any and Grade 3 or higher non-hematologic toxicities, summarize length of hospitalization time, and to estimate count recovery. This study will utilize the CTCAE version 4.03 of the NCI for toxicity grading.

10.7.2. Adverse Events

Adverse events will be coded according to the Medical Dictionary for Regulatory Activities (MedDRA) (updated version). The severity of AEs will be graded according to the NCI-CTCAE (version 4.03, June 2010).

Treatment-emergent adverse events are defined as any AE occurring or worsening on or after the first treatment of the study medication and within 28 days after the last dose. All TEAEs, AEs leading to study medication discontinuation, AEs leading to dose reduction/interruption, AEs related to the lenalidomide, SAEs and AE leading to death will be summarized by cycle and 28-day period after last cycle as well as by subject (worse recorded grade) per event type (organ class and preferred term) and grade. A summary of AEs with NCI-CTCAE Grade 3 or higher, as well as the most frequent preferred terms will also be provided by grade and term.

10.7.3. Deaths

Deaths during study treatment (defined as deaths, which occur starting from the first dose and within 28 days after the last dose of study medication) and during the Follow-up Phase shall be summarized by frequency of occurrence and corresponding percentage by cause of death per period (during Treatment or Follow-up Phases) as well as overall.

10.7.4. Clinical Laboratories

Clinical laboratory adverse events will be graded according to NCI-CTCAE (version 4.03, June 2010) for applicable tests. Baseline grade and worst grade during study treatment for selected laboratory results will be summarized. Shift from baseline to the worst grade observed during the study treatment for selected laboratory results will also be provided.

10.7.5. Vital Signs

For vital signs, shift from baseline to worst during the treatment in below, within, and above the normal ranges will be displayed in cross-tabulations. Summary statistics (N, mean, standard deviation, median, minimum, and maximum) of observed and change from baseline values will be presented.

been collected to review safety and treatment activity data. This close monitoring for safety of the IP will ensure a low exposure rate of the IP to subjects by ensuring the boundary of considered acceptable toxicity is not crossed.

10.9.1. Stopping Criteria for Acute Graft-Versus-Host Disease

Subjects who are post-allogeneic HSCT will be monitored closely for the development of acute graft-versus-host disease (GVHD). While Grade 1 to 2 GVHD will be tolerated, if 40% or more of subjects develop Grade 3 or higher GVHD, lenalidomide at this dose will be deemed intolerable for subjects who are post-HSCT.

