The primary objective of this study is to determine the activity of lenalidomide in pediatric patients with relapsed/refractory AML (with second or greater relapse or refractory to at least 2 prior induction attempts). Treatment of an AML recurrence following allogeneic HSCT commonly includes a rapid taper of immune-suppression used for prophylaxis and/or treatment of acute GVHD. In this setting, mild GVHD is an expected and a desirable toxicity. The use of the immune-modulatory drug, lenalidomide, in patients at risk for acute GVHD will be challenging but with the potential for benefit to the patient with induction of mild but manageable GVHD. Accordingly, this study will attempt to keep patients with new mild GVHD on protocol therapy, while recognizing that Grade 3 or greater acute GVHD will be an unacceptable toxicity. First, patients with active GVHD or requiring immune-suppression including steroids for GVHD control are not eligible for enrollment. Patients with a history of Grade 3 or greater GVHD or those on therapeutic dosing of immune suppressive therapy will be discussed with the study chair prior to enrollment and require a longer observation time off immune-suppression prior to enrollment (4 weeks) compared to those without a history of severe GVHD or who are already on tapering dosing of immune suppressive therapy without signs of GVHD (2 weeks off immune-suppression) (see Sections 6.25, 7.2 and 8.2.1). Second, patients who develop Grade 3 or greater GVHD, or lower grade GVHD that does not respond to protocol prescribed interventions (Section 8.2.1) will be off study treatment. No dose reduction is planned as it is not clear that this toxicity would improve and be altered by dose adjustment. Incidence of GVHD will be closely monitored and the study will be closed to post-HSCT patients if stopping thresholds for Grade 3 or greater GVHD are crossed (see Section 10.9.1). Patients will be monitored for development of chronic GVHD.

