 - If residual leukemia is demonstrated, which is stable from prior assessments (ie, subject with previous PR/treatment failure), the subject will proceed to the next cycle of lenalidomide as scheduled without delay and without regard to peripheral blood counts. Lenalidomide dose will NOT be decreased.

Special Instructions for Management of Graft Versus Host Disease (GVHD):

Post-HSCT subjects will be monitored closely for development of GVHD of the skin, liver, or gut, see [Appendix K](#) for grading criteria.

- Subjects with Grade 1 or 2 GVHD (any site, biopsy proven or probable, ie, requires systemic steroid treatment) will be managed at the discretion of the local bone marrow transplant (BMT) physician and lenalidomide will be held.
 - If the acute GVHD resolves within 14 days and the subject is being treated with no more than topical therapies and/or up to 0.5 mg/kg/day corticosteroids (prednisone equivalents), lenalidomide will be restarted at the same prior dose.
 - After 14 days, subjects requiring more than 0.5 mg/kg/day corticosteroids or other systemic therapy (ie, not including topical therapies) to manage the acute GVHD will be discontinued from the study.
- Subjects with Grade 3 or 4 GVHD (any site, suspected or biopsy proven) will have lenalidomide discontinued permanently and will be managed at the discretion of the local HSCT physician. These subjects will be discontinued from the study.

Guidelines for Renal Insufficiency

- Lenalidomide is primarily excreted unchanged by the kidney; therefore, study treatment will be held for subjects who experience CLcr < 70 mL/min (confirmed by repeat creatinine measurement within 3 days). If CLcr returns to levels that meet initial eligibility criteria (> 70 mL/min) within 7 days of IP interruption, the subject may resume treatment at a full dose. However, if the subject improves within 14 days, a dose reduction by 1 dose level of study treatment will be considered at the discretion of the Investigator, and after careful consideration of the subject's renal impairment etiology and the subject's tolerability to lenalidomide. If toxicity does not resolve to eligibility by 14 days of dose interruption, then the subject will be off study treatment.

Dose Discontinuation:

- Subjects experiencing a thromboembolic event unrelated to a central line will be discontinued from lenalidomide treatment.

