10.9.2. Statistical Rationale for GVHD Stopping Criteria

The GVHD stopping rule is designed so that the trial will stop rarely when the true GVHD rate is 10% and frequently when the true GVHD rate is 40% ($H_0: p = 0.10$, $H_1: p = 0.40$, and $\alpha = 0.10$, power is 90%). In this case, if 4 or more post-HSCT subjects in the first 15 develop Grade 3 or 4 GVHD, the stopping rule threshold would be crossed and further post-HSCT subjects would not be enrolled.

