11.6. Rates of acute and chronic graft-versus-host disease (GVHD)

Graft-versus-host disease (GVHD) will be summarized as collected in the “Adverse Events” eCRF page with the following preferred terms: “Acute graft versus host disease”, “Chronic graft versus host disease” and “Overlap syndrome”.

The incidence of GVHD TEAEs will be summarized by maximum CTCAE grade (1 or 2, higher than 2) within type of GVHD (overall, overlap, acute, chronic and overlap + acute GVHD).

Safety population subjects that had previous transplant (as collected in the “Stem Cell Transplants” eCRF page) will be selected for these summary tables and their total number will be used as denominator for the computation of incidence rates.

GVHD data as collected in the “GVHD” eCRF page will also be listed.

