14. INTERIM ANALYSIS

Periodic reports (at least semi-annually) will be provided to an external data monitoring committee (DMC). The first DMC meeting will be held after 4 subjects have completed at least 1 cycle of study treatment, if having not stopped therapy earlier due to a safety issue, in order to evaluate safety and provide a recommendation.

An interim analysis is planned to take place, at the end of Stage 1, once the first 18 subjects evaluable for the primary endpoint have been accrued and completed up to 4 cycles of lenalidomide treatment if they have not stopped therapy before 4 cycles, ie, the RR population. The interim analysis will assess the number of subjects with CR or CRi under lenalidomide treatment. If fewer than 3 of 18 subjects achieve a response then the study will be closed; otherwise the study shall continue as planned and enrollment shall continue into Stage 2.

At the interim analysis, only a subset of the summary outputs detailed in this SAP will be produced. No figures and listings will be provided, with the exception of AE listings. These summaries will include: analysis populations, subject disposition, demography and baseline characteristics, concomitant medications and procedures, morphological complete response rate within the first four cycles of treatment, overall response rate, summary of disease assessment outcome, summaries on exposure to lenalidomide, TEAE, TEAE with CTCAE grades 3 or 4, TEAE with CTCAE grade 3 or 4 related to lenalidomide, TEAE with CTCAE grade 5, cause of death during treatment period and cause of death after 28 days of end of treatment.

Should the study stop after Stage 1 then the primary final analysis will take place.

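### The acute GVHD stopping threshold is 40% or more in Protocol 10.9.1 but 4 of the first 15 (26.7%) in 10.9.2; only the latter meets the stated alpha and power

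*Protocol*

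**What the plan says.** Protocol 10.9.1 states the criterion as a percentage, with no denominator and no schedule of looks: "if 40% or more of subjects develop Grade 3 or higher GVHD, lenalidomide at this dose will be deemed intolerable for subjects who are post-HSCT".

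Protocol 10.9.2 states it as a count: "if 4 or more post-HSCT subjects in the first 15 develop Grade 3 or 4 GVHD, the stopping rule threshold would be crossed", after which no more post-HSCT subjects are enrolled. The same section gives the design inputs: a true rate of 10% under the null hypothesis, 40% under the alternative, alpha 0.10 and power 90%. Here 40% is a true rate, not a cut-off for observed data.

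Protocol 1.4.2 announces the rule and cites only the first of the two sections: "the study will be closed to post-HSCT patients if stopping thresholds for Grade 3 or greater GVHD are crossed (see Section 10.9.1".

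The SAP does not choose between them. Of the Stage 1 analysis, Section 14 says: "The interim analysis will assess the number of subjects with CR or CRi under lenalidomide treatment". It contains no GVHD rule. Section 11.6 is descriptive: "The incidence of GVHD TEAEs will be summarized by maximum CTCAE grade (1 or 2, higher than 2) within type of GVHD".

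The grade wording also differs: Grade 3 or higher in 10.9.1, Grade 3 or 4 in 10.9.2.

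**The concern.** A safety boundary needs one value. Four of 15 is 26.7% and 5 of 15 is 33.3%. Both cross the boundary in 10.9.2, and neither reaches 40%. A data monitoring committee with either count in front of it would find one section telling it to close post-HSCT enrolment and another, under the heading for stopping criteria, telling it that the threshold has not been reached. Section 1.4.2 directs the reader to the second of these.

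The likely origin is that the 40% true rate under the alternative was carried into 10.9.1 as if it were the observed trigger. The effect is to raise the bar for stopping.

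At stake is whether further children who have had a transplant are exposed while severe GVHD accumulates. Management of the individual child is not in doubt, since Protocol 8.2.1 is clear: "Subjects with Grade 3 or 4 GVHD (any site, suspected or biopsy proven) will have lenalidomide discontinued permanently". Only the decision to close enrolment is ambiguous.

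**Working it through.** **Inputs.** From Protocol 10.9.2: n = 15, cut-off r = 4, null rate p0 = 0.10, alternative rate p1 = 0.40, alpha 0.10, power 0.90. From Protocol 10.9.1: observed proportion of 40% or more, which at n = 15 means 0.40 × 15 = 6 or more.

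**Formula.** With X the number of severe GVHD cases among 15 subjects, P(X ≥ r) = 1 − Σ (k = 0 to r − 1) C(15,k) p^k (1 − p)^(15 − k). Checking the 4-of-15 rule as subjects accrue does not change this probability, because a count that has reached 4 cannot fall.

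**Step 1: reproduce the plan's rule (4 of 15).**
- p = 0.10: 1 − (0.2059 + 0.3432 + 0.2669 + 0.1285) = 0.0556 (unrounded terms).
- p = 0.40: 1 − (0.0005 + 0.0047 + 0.0219 + 0.0634) = 0.9095.

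Both targets are met. The neighbouring cut-offs fail: 3 of 15 gives 0.184 and 0.973 (alpha too high), and 5 of 15 gives 0.013 and 0.783 (power too low). So 4 is the only cut-off at n = 15 that meets both.

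**Step 2: apply 10.9.1 at the same n (6 of 15).**
- p = 0.10: P(X ≥ 6) = 0.0022.
- p = 0.40: P(X ≥ 6) = 0.5968.

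Alpha is met; power is 90 − 59.7 = 30.3 percentage points short.

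**Step 3: how often the sections disagree at the 15th subject (4 or 5 cases).**
- p = 0.40: 0.1268 + 0.1859 = 0.3127.
- p = 0.10: 0.0428 + 0.0105 = 0.0533.

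**Step 4: a more favourable reading of 10.9.1.** Since 10.9.1 gives no denominator, it could be read as a running proportion, checked after every subject from the m-th to the N-th and crossed as soon as cases/n ≥ 0.40. The number of post-HSCT subjects is not given, so I assumed N between 15 and 47, the latter being the protocol's maximum enrolment. Exact recursion over the count gives:

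| First look (m) | Alpha, N = 15 / 47 | Power, N = 15 / 47 |
|---|---|---|
| 1st subject | 0.2164 / 0.2165 | 0.8577 / 0.9176 |
| 5th subject | 0.0874 / 0.0875 | 0.8043 / 0.8882 |
| 10th subject | 0.0138 / 0.0139 | 0.7043 / 0.8393 |

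Over every first look m from 1 to N and every N from 15 to 47, no schedule has alpha ≤ 0.10 together with power ≥ 0.90. The highest power with alpha ≤ 0.10 is 0.8882 (first look at the 3rd to 5th subject, N = 47).

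**The case against.** The strongest reply is that only 10.9.2 can be carried out. It follows directly on 10.9.1, is labelled as its rationale, and supplies the count, the denominator and the action, whereas 10.9.1 has no denominator and no look schedule. A committee reading both would probably use 4 of 15, and the chance of stopping at a true 40% is then at least 90.9%. It is also possible that 10.9.1 meant the true rate. All of this is fair, and it limits the harm: power is lost only if 10.9.1 is used alone. It does not remove the conflict. The wording of 10.9.1 describes the share of subjects who develop GVHD, which is an observed proportion, and 1.4.2 names that section as the source of the threshold. If a true rate was meant, 10.9.1 contains no usable criterion and still needs rewording.

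A second reply is that both could apply: 4 of the first 15, plus 40% as a continuing check. With the 40% check starting at the 15th subject and running to 47, this gives alpha 5.6% and power 93.0%, inside both targets. With the check starting at the 5th subject, alpha is 11.3%, which exceeds 0.10. The plan states neither the combination nor the schedule. What stands is that 10.9.2 is silent after the 15th subject, so the sponsor should decide deliberately whether anything applies later.

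Third, the grade difference may be empty if the GVHD scale ends at Grade 4; the grading appendix is not in the available text. That point is minor. The opening of Section 10.9 and the committee's charter are also unavailable and might say how the rule is applied, but both threshold sentences are complete as printed. The SAP's silence is not in itself an error; it means only that the SAP does not resolve the difference.

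**Conclusion.** The concern holds: 10.9.1 is wrong as written, and the design in 10.9.2 is sound. At 15 post-HSCT subjects the two thresholds stop with probability 90.9% (4 of 15) and 59.7% (6 of 15) when the true rate is the unacceptable 40%, and they give opposite answers with probability 31.3%. At a true rate of 10% they disagree with probability 5.3%.

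These figures assume independent subjects with a common GVHD rate and at least 15 post-HSCT subjects enrolled. The 59.7% further assumes that 10.9.1 is applied alone and once, at n = 15. Running checks of 10.9.1 do better, but none considered meets both targets for 15 to 47 subjects. Because this is a safety boundary for children and the section cited for it carries the wrong figure, it must be corrected.

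**What to change.** Restate the criterion in 10.9.1 as *4 or more of the first 15 post-HSCT subjects with Grade 3 or higher acute GVHD*. Use the same grade and acute-GVHD wording in 10.9.2. Keep 40% only in 10.9.2, as the unacceptable true rate under the alternative hypothesis. The reference in 1.4.2 then points to the right rule without being changed.

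The cost is an edit to two sections. No new data are needed, and the 4-of-15 rule, the sample size and the primary decision rule stay as they are. If the sponsor also wants a criterion after the 15th post-HSCT subject, that would be an addition to the design and should be written with its own denominator, look schedule and operating characteristics.

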10.9.2. Statistical Rationale for GVHD Stopping Criteria

The GVHD stopping rule is designed so that the trial will stop rarely when the true GVHD rate is 10% and frequently when the true GVHD rate is 40% ($H_0: p = 0.10$, $H_1: p = 0.40$, and $\alpha = 0.10$, power is 90%). In this case, if 4 or more post-HSCT subjects in the first 15 develop Grade 3 or 4 GVHD, the stopping rule threshold would be crossed and further post-HSCT subjects would not be enrolled.

10.10. Pharmacokinetic Analysis

Approximately 50% of subjects should be younger than 12 years of age to provide adequate PK data for this age subset. Lenalidomide concentration data from this study will be combined with the concentration data from other pediatric studies and literature data to perform a population pharmacokinetic analysis. Main pharmacokinetic parameters in plasma to be estimated include AUC, C_{max} , apparent clearance, and apparent volume of distribution. Effect of age and body size on lenalidomide PK will be assessed. Other relevant covariates for the main PK parameters may be identified. The between-subject variability for PK parameters will be estimated. If data allow, main PK parameters (clearance and volume of distribution) will be summarized by age as appropriate (eg, 1 to < 6, 6 to < 12, and 12 to \leq 18 years).

Non-compartmental PK parameters in plasma may also be estimated using intensive lenalidomide concentration data collected from this study.

10.11. Other Topics

Not Applicable.

11. ADVERSE EVENTS

11.1. Monitoring, Recording and Reporting of Adverse Events

An AE is any noxious, unintended, or untoward medical occurrence that may appear or worsen in a subject during the course of a study. It may be a new intercurrent illness, a worsening concomitant illness, an injury, or any concomitant impairment of the subject's health, including laboratory test values (as specified by the criteria below), regardless of etiology. Any worsening (ie, any clinically significant adverse change in the frequency or intensity of a pre-existing condition) should be considered an AE. A diagnosis or syndrome should be recorded on the AE page of the CRF rather than the individual signs or symptoms of the diagnosis or syndrome.

Abuse, withdrawal, sensitivity or toxicity to an investigational product should be reported as an AE. An overdose, accidental or intentional, whether or not it is associated with an AE should be reported on the overdose CRF. For the definition of overdose see Section 8.2.2. Any sequelae of an accidental or intentional overdose of an investigational product should be reported as an AE on the AE CRF. If the sequelae of an overdose is an SAE, then the sequelae must be reported on an SAE report form and on the AE CRF. The overdose resulting in the SAE should be identified as the cause of the event on the SAE report form and CRF but should not be reported as an SAE itself.

In the event of overdose or exaggerated response, the subject should be monitored as appropriate and should receive supportive measures as necessary. There is no known specific antidote for a lenalidomide overdose. Actual treatment should depend on the severity of the clinical situation and the judgment and experience of the treating physician.

All subjects will be monitored for AEs during the study. Assessments may include monitoring of any or all of the following parameters: the subject's clinical symptoms, laboratory, pathological, radiological or surgical findings, physical examination findings, or other appropriate tests and procedures.

All AEs will be recorded by the Investigator from the time the subject signs ICF/IAF until 28 days after the last dose of IP, as well as those SAEs made known to the Investigator at any time thereafter that are suspected of being related to IP. Adverse events and SAEs will be recorded on the AE page of the CRF and in the subject's source documents. All SAEs must be reported to Celgene Drug Safety within 24 hours of the Investigator's knowledge of the event by facsimile, or other appropriate method, using the SAE Report Form, or approved equivalent form.

11.2. Evaluation of Adverse Events

A qualified Investigator will evaluate all AEs as to:

11.2.1. Seriousness

An SAE is any AE occurring at any dose that:

- Results in death;
- Is life-threatening (ie, in the opinion of the Investigator, the subject is at immediate risk of death from the AE);

- Requires inpatient hospitalization or prolongation of existing hospitalization (hospitalization is defined as an inpatient admission, regardless of length of stay);
- Results in persistent or significant disability/incapacity (a substantial disruption of the subject's ability to conduct normal life functions);
- Is a congenital anomaly/birth defect;
- Constitutes an important medical event.

Important medical events are defined as those occurrences that may not be immediately life threatening or result in death, hospitalization, or disability, but may jeopardize the subject or require medical or surgical intervention to prevent one of the other outcomes listed above. Medical and scientific judgment should be exercised in deciding whether such an AE should be considered serious.

Second primary malignancies will be monitored as events of interest and must be reported as SAEs regardless of causal relationship to IP. This includes any SPM, regardless of causal relationship to IP, occurring at any time for the duration of the study, from the time of signing the ICF/IAF up to 5 years from the date of the last subject's first dose unless withdrawal of consent, lost to follow-up or death. Events of SPM are to be reported using the SAE report form and must be considered an "Important Medical Event" even if no other serious criteria apply; these events must also be documented in the appropriate page(s) of the CRF and subject's source documents. Documentation on the diagnosis of the second primary malignancy must be provided at the time of reporting as an SAE (eg, any confirmatory histology or cytology results, X-rays, CT scans, etc.).

Events **not considered** to be SAEs are hospitalizations for:

- a standard procedure for protocol therapy administration. However, hospitalization or prolonged hospitalization for a complication of therapy administration will be reported as an SAE.
- routine treatment or monitoring of the studied indication not associated with any deterioration in condition.
- the administration of blood or platelet transfusion as routine treatment of studied indication. However, hospitalization or prolonged hospitalization for a complication of such transfusion remains a reportable SAE.
- a procedure for protocol/disease-related investigations (eg, surgery, scans, endoscopy, sampling for laboratory tests, bone marrow sampling). However, hospitalization or prolonged hospitalization for a complication of such procedures remains a reportable SAE.
- hospitalization or prolongation of hospitalization for technical, practical, or social reasons, in absence of an AE.
- a procedure that is planned (ie, planned prior to start of treatment on study); must be documented in the source document and the CRF. Hospitalization or prolonged hospitalization for a complication remains a reportable SAE.

- an elective treatment of or an elective procedure for a pre-existing condition, unrelated to the studied indication, that has not worsened from baseline.
- emergency outpatient treatment or observation that does not result in admission, unless fulfilling other seriousness criteria above.

If an AE is considered serious, both the AE page/screen of the CRF and the SAE report form must be completed.

For each SAE, the Investigator will provide information on severity, start and stop dates, relationship to the IP, action taken regarding the IP, and outcome.

